containing 250 chips that are assigned a certain value. Two-hundred thirty chips denote a small amount (\$1.00), 18 chips denote a moderate amount (\$10.00), one chip denotes a large amount (\$50.00), and one chip denotes a jumbo amount (\$100.00). Participants will be allowed three draws at the screening visit if they provide a UDS and five draws at subsequent visits if their saliva drug screens are negative. Participants will be paid with a Greenphire ClinCard.

Total possible reimbursement is \$295/participant plus the sum of what is gathered from the chip pick.

[figure not shown]
D4.i. Confidentiality: Confidentiality of all research data will be maintained by keeping all data in a locked file, limiting access to the computer database to only study personnel, and by using patient code numbers/initials as opposed to names on all paperwork. Any requests for the release of patient information will be referred to the candidate.

D4.i. Study Timeline

	Screen	BL/ Wk1	Wk 2	Wk 3	Wk 4	1 Month FU	6 Month FU
MINI	x						
DSM-5 CUD criteria		x			x	x	x
Urine pregnancy test	x	x			x		
Urine cannabinoid test, TLFB, CWS, PSQI, Menstrual History, HAM-A, HAM-D	x	x	x	x	x	x	x
MJ Summary Sheet, Self-reports	x	x			x	x	x
Neuropsych testing, Digit Span, SDMT		x			x	x	
Approach Bias assessment, Cue reactivity			x		x	x	
Integrated Treatment (MET/CBT + ABM)*		x	x	x	x		

*Participants will receive three sessions of MET/CBT over the four weeks.

D4.j. Study visit flow chart

D5. Statistical Considerations.

General Analysis: Baseline clinical and demographic characteristics will be collected and contrasts performed between treatment groups. Continuous and ordinal characteristics will be compared using a Wilcoxon Rank-Sum test while categorical characteristics will be compared using a Pearson Chi-Square test. In addition to baseline treatment group differences, preliminary analysis of baseline characteristics will examine significant correlates of outcomes. Characteristics found to be significantly associated with the primary outcome measures, will be included as covariates in the initial stages of adjusted model development. All analyses will be performed on the intent-to-treat sample consisting of all randomized subjects.

Study Aims: Aim 1 is to evaluate the efficacy of ABM in the reduction of cannabis cue reactivity outcomes between BL and EOT/FU, as well as the variance around each estimate. Generalized linear mixed (GLM) effects regression

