models will be used to estimate each parameter and variance estimate of ABM or sham-ABM on cue reactivity measured at EOT and FU visit. Model based means and associated standard errors will be used to assess treatment group differences at EOT and FU. These methods are particularly well suited in instances where missing data is present. Aim 2 is to evaluate the efficacy of ABM on the reduction of cannabis use characteristics between BL and EOT/FU, as well as the variance around each estimate. Cannabis use data will be collected using the TLFB (proportion of use days, abstinence) and creatinine-adjusted cannabinoid levels (CN-THCCOOH) and will be compared between treatment groups using GLM models with appropriate distributional assumptions. Study data will be modeled as time invariant summary measures of the use at the end of the 4-week study period. Secondarily, we will also assess the efficacy of ABM on abstinence at FU (four-week abstinence). Study abstinence will be determined using UDS results (≤ 50 ng/ml) in concert with daily self-reported use. Exploratory Aim 1 will investigate the influence of gender on the treatment outcome and parameter estimates. Model interaction terms between study treatment assignment and gender will be added to each model developed for study aims 1 and 2 and tested for evidence of effect modification. When gender modification is present, pairwise comparisons within and across groups will be examined to assess the direction and magnitude of the modification. Additional analysis will assess neuropsychological data between groups over time using GLM models with appropriate distributions. Relative improvements over time associated with ABM will be assessed using between group comparisons taken at EOT and FU visits while controlling for baseline response data. Continuous outcome data will be assessed using a Gaussian distribution and count data will be assessed using a Poisson distribution. Second, neuropsychological data will be incorporated in the primary outcome models using interactions with treatment assignment to assess possible moderating effects on reported cannabis craving and use. Lastly, when ABM shows a significant relationship with changes in cannabis craving and use, neuropsychological measures will be assessed for mediating effects on the significant outcomes using bootstrap methods⁴⁵. All analyses will be conducted using SAS v. 9.4.

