Randomization: Participants will be randomized by study personnel to receive either active- or sham-ABM training using a stratified random block design. The randomization will be stratified on (1) gender and (2) baseline daily cannabis use intensity (less than 1 session or 1 and above). The purpose of stratification is to distribute these covariates equally across treatment groups. Study therapists and all personnel responsible for data analysis or interpretation will be blinded to group assignment. Only research personnel administering the ABM sessions will be unblinded.

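### D5 picks covariates for the Aim 1 and Aim 2 models by significance, prespecifies neither the baseline outcome nor the randomisation strata, and does not say which model is primary

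*Combined protocol and SAP*

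**What the plan says.** All the relevant text is in D5.

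- **General Analysis.** Baseline characteristics are first screened as correlates of the outcomes. Then: "Characteristics found to be significantly associated with the primary outcome measures, will be included as covariates in the initial stages of adjusted model development". There is no significance threshold, no candidate list, and no rule for what stays after those initial stages.
- **Aim 1.** The aim is to "evaluate the efficacy of ABM in the reduction of cannabis cue reactivity outcomes between BL and EOT/FU". The mixed model is to "estimate each parameter and variance estimate of ABM or sham-ABM on cue reactivity measured at EOT and FU visit", and "Model based means and associated standard errors will be used to assess treatment group differences at EOT and FU". No baseline term or stratum is named.
- **Aim 2.** Timeline Follow-Back (TLFB) use and creatinine-adjusted cannabinoid level (CN-THCCOOH) "will be compared between treatment groups using GLM models with appropriate distributional assumptions", as one summary at the end of the four weeks. Again no baseline term or stratum is named, although this aim too is worded as a reduction from baseline.
- **Neuropsychological data.** Only here does D5 write baseline control: groups are compared at end of treatment (EOT) and follow-up (FU) "while controlling for baseline response data".
- **Gender.** It enters only through the treatment-by-gender interaction of Exploratory Aim 1.
- **Randomization.** "The randomization will be stratified on (1) gender and (2) baseline daily cannabis use intensity (less than 1 session or 1 and above". The use-intensity stratum appears in no model. On blinding: "Study therapists and all personnel responsible for data analysis or interpretation will be blinded to group assignment".

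**The concern.** The aims concern change from baseline and the baseline values are planned data, yet the models that test the aims do not commit to using them. Two things are at stake.

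The first is precision. A baseline measure of the same outcome is usually the strongest predictor available, and leaving it out widens the interval for the treatment effect. Whether it enters here depends on an undefined screen.

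The second is that the primary result is not fixed. An unadjusted estimate and estimates screened at different thresholds all fit the text, and they can fall on different sides of 5%. The trial's variance estimate, which the power section intends for planning the next trial, also depends on which covariates are in the model.

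**Working it through.** **Inputs.** From Statistical Power and Sample Size: d = 0.58, within-subject correlation 0.8, 84 completers (42 per arm), 80% power, 5% type I error (two-sided assumed), 20% attrition, 106 randomised. The baseline-outcome correlation r is not given; 0.3, 0.5 and 0.7 are assumed.

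**1. The plan's own figure.** The mean of two measures correlated 0.8 has variance (1 + 0.8)/2 = 0.90. Then n per arm = 2 × (1.96 + 0.8416)² × 0.90 / 0.58² = 42.0, so 84. Attrition gives 84/0.80 = 105, made even as 106. The figure reproduces with no baseline or stratum term.

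**2. Adding a prespecified baseline term** (d on the unadjusted SD).

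- EOT+FU mean: residual variance 0.90 − r², so effective d = 0.58/√(0.90 − r²) and power = Φ(effective d × √(42/2) − 1.96). At r = 0, 0.58/√0.90 = 0.611, × 4.583 = 2.80, Φ(0.84) = 0.80. At r = 0.5, 0.58/√0.65 = 0.719, × 4.583 = 3.30, Φ(1.34) = 0.91.
- Single visit: effective d = 0.58/√(1 − r²), t-based. This matters because group differences are to be assessed at EOT and at FU.

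| r | EOT+FU power | CI width ratio | Single-visit power | CI width ratio |
|---|---|---|---|---|
| 0 (no baseline) | 0.800 | 1 | 0.748 | 1 |
| 0.3 | 0.840 | 0.949 | 0.786 | 0.954 |
| 0.5 | 0.909 | 0.850 | 0.858 | 0.866 |
| 0.7 | 0.986 | 0.675 | 0.957 | 0.714 |

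The two power columns use different approximations. On the normal basis the single-visit values are 0.757, 0.796, 0.866 and 0.961; on the t basis EOT+FU without baseline is 0.791.

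**3. If baseline is already a screening candidate.** Simulation of 10,000 runs per cell: 42 per arm, allocation balanced in the 2×2 strata, one stratum correlated 0.2 with outcome, 20 irrelevant candidates.

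| r | Prespecified | Screened, p<0.05 | Gain (points) | Baseline selected, p<0.05 | Screened, p<0.20 |
|---|---|---|---|---|---|
| 0.3 | 0.842 | 0.816 | 2.6 | 80% | 0.791 |
| 0.5 | 0.918 | 0.910 | 0.8 | 99.9% | 0.887 |
| 0.7 | 0.989 | 0.987 | 0.2 | 100% | 0.982 |

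At p<0.20 the gain is 5.1, 3.1 and 0.7 points.

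**4. If d = 0.58 is on a baseline-adjusted scale.** The unadjusted SD is then larger by 1/√(1 − r²), so a model without baseline has effective d = 0.58 × √(1 − r²)/√0.90. EOT+FU power is 0.762, 0.680 and 0.516 at r = 0.3, 0.5 and 0.7.

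**5. Strata alone.** With an assumed stratum-outcome correlation of 0.2, power moves from 0.800 to 0.818 (EOT+FU) and from 0.748 to 0.764 (single visit).

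**6. Open choice of model.** With no true effect, each single strategy in the simulation of step 3 rejected in 4.6% to 5.5% of runs. Counting a rejection by either the unadjusted or the screened (p<0.05) model gave 6.7%, 7.4% and 8.4% at r = 0.3, 0.5 and 0.7. A separate 20,000-run check of unadjusted against baseline-adjusted gave 6.3%, 7.4% and 8.3%. At d = 0.58 the unadjusted and screened models disagreed on significance in 8.1%, 12.7% and 16.5% of runs.

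**The case against.** **The plan may already use baseline.** The screen covers baseline clinical characteristics, and baseline craving, cannabinoid level and use fit that description. Nothing bars them. On that reading the lost power nearly vanishes for r of 0.5 or more (step 3). This stands, and it limits the size of the point. It does not settle which model is primary.

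**The baseline-control phrase might extend to Aims 1 and 2.** By position it belongs to the neuropsychological analysis, with neuropsychological text on both sides. At best this leaves the plan ambiguous.

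**A reader might infer inflated type I error.** Letting the threshold, the adjustment and the candidacy of baseline all vary gives up to 11.0% at r = 0.7. That needs six models compared freely and any significant one reported. The plan proposes no such thing, any one strategy fixed in advance holds about 5%, and analysts are blinded. Blinding does not remove the risk, because coded arms still yield p-values.

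**A reader might infer that Aim 1 is underpowered, or equally that adjustment is purely a bonus.** Neither is established. The planned N reproduces at 80% without baseline, but only if d = 0.58 is on the unadjusted SD. The Figure 1 caption in Section C describes pilot craving as baseline-adjusted. That may suggest the other scale, but does not settle it.

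**This is a pilot.** True, and the power section says preliminary data are the main purpose. The same section also claims adequate power for the primary aims, so naming the model is a fair request.

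**Conclusion.** The point holds as a specification gap with an inexpensive better alternative. D5 selects covariates by their significance with the outcome, commits to neither the baseline outcome nor the strata in the main models, and leaves the primary model unnamed.

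The size depends on how the plan is read. Against a model that never includes baseline, prespecification raises EOT+FU power from 80% to about 84%, 91% and 99% (single visit 75% to 79%, 86% and 96%). Against a p<0.05 screen that includes baseline, the gain is about 0.2 to 3 points. If d = 0.58 is baseline-adjusted, a model without baseline would have about 76%, 68% and 52%. Free choice between unadjusted and adjusted models would put type I error at about 6-8%. All these figures rest on the assumed r, on 42 completers per arm and on a Gaussian outcome; the screening and type I results also rest on the simulation settings.

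One further inference should be avoided. The timeline table as extracted marks cue reactivity at Wk 2, which might suggest a baseline taken after training began. D1 and D4.e place it at baseline, E.1.c puts cue exposure before therapy, and D1 puts ABM after therapy. The mark may be an extraction artefact.

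**What to change.** In D5:

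1. For cue reactivity, CN-THCCOOH and proportion of use days, name as primary a model with treatment, visit and treatment-by-visit (where repeated), the baseline value of the same outcome, gender and the use-intensity stratum. State that no covariate is added or removed because of its association with the outcome.
2. Score baseline in the same way as the outcome. D4.e takes craving three times per session, so say whether the post-cannabis-cue score or a difference is used, and apply it at every visit.
3. Move significance-selected covariates (with a stated threshold) and the time-varying sleep index (PSQI, D4.f) to labelled sensitivity analyses.
4. For abstinence, adjust for baseline 30-day TLFB use and gender. Include the use-intensity stratum only if it is estimable, or use a penalised (Firth) logistic model. The documents give neither abstinence rates nor stratum sizes. If 5-10% are abstinent and 5-10% of 84 completers fall in the smaller stratum (assumed), that stratum is empty or shows no outcome variation in about 43-82% of simulated trials.
5. Use baseline cue reactivity as a covariate only if it is measured before the first ABM session. Reconcile D1, D4.e and E.1.c with the timeline table.
6. State whether d = 0.58 is on the raw or the baseline-adjusted scale.

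**Cost.** Wording only, since these baseline measures are already planned, subject to item 5 for cue reactivity. The added terms use about three degrees of freedom, less than 0.1 point of power for a Gaussian outcome. For logit-link outcomes the estimate becomes conditional rather than marginal, and its interval need not narrow.

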Experience with recruitment and retention of adults with CUD: [name] (primary mentor), has completed multiple NIH-funded studies involving individuals with CUD. Of immediate relevance to the proposed project, the candidate recently completed a 4-session human laboratory pilot study in non-treatment seeking adults with CUD. Over the course of approximately 8 months, a total of 61 patients were consented, of which, 49 were randomized, 39 (80%) completed all 4 study sessions, and 33 (67%) completed through follow-up. These studies demonstrate the ability to effectively recruit and retain individuals with CUD for brief interventions.

Experience with adjunctive treatments for psychosocial interventions: Developing adjunctive treatments for CUD has been a career research focus of primary mentor [name]. Most recently, she completed a pilot study on oxytocin-enhanced MET for cannabis dependence²⁶. Participants who received MET plus oxytocin demonstrated reductions in amount (grams) used daily ($p=0.012$) and number of cannabis sessions per day ($p=0.003$), while those who received MET plus placebo did not. In addition to [name] experience, off-site mentor [name] also has considerable expertise integrating psychosocial interventions with novel adjunctive treatment approaches (see *Biosketch*).

Experience with the ABM paradigm: The candidate recently completed a randomized sham-controlled pilot study investigating the effect of ABM in non-treatment seeking adults with CUD (N=33). Results showed a trend of blunted cannabis cue-induced craving at end of treatment among ABM participants compared to controls ($p=0.051$) (see Figure 1), and preliminary evidence of gender modification of cannabis outcomes; men receiving ABM reported fewer sessions per day at the end of treatment (EOT) compared to women ($p=0.022$), while there was no gender

difference in the sham-control group (Figure 2). These pilot findings suggest that ABM may be efficacious in reducing cue-reactivity and improving cannabis outcomes, and that gender may

Figure 1: Cannabis craving by group and visit adjusted for baseline.

[figure not shown]
[figure not shown]

Figure 2: Cannabis use by gender and condition at EOT.

moderate this effect. As proposed in this K23 application, further investigation into the feasibility and efficacy of ABM as a potential adjunct to psychosocial treatments is warranted.

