Statistical Power and Sample Size: The proposed study is largely focused on obtaining preliminary data to inform and power a larger randomized controlled trial to assess ABM for CUD. However, the proposed sample size will allow for adequate power to assess the primary study aims. Primary AIM 1: Evaluate the efficacy of ABM combined with MET/CBT on cue-reactivity in adults with CUD. In a previous pilot study, we found evidence of greater reductions in cue induced cannabis craving at the end of treatment in those receiving active ABM as compared to sham ABM (MCQ: 43.2 ± 1.0 vs. 39.5 ± 1.0 , $\Delta = 3.7 \pm 1.4$, $d = 0.58$). We assume that the effect will be similar in the proposed study; however, we will measure use during the final treatment visit as well as at the FU visit. Under a correlated measures model assumption with a conservative within subjects correlation of $\rho = 0.8$, a sample size of 84 participants would be necessary to detect the noted treatment effect size with 80% power and a type 1 error rate of 5%. To account for an expected attrition of 20% based on our pilot study we have inflated our sample size to **106 participants (n=53 in each treatment assignment)**. To achieve a randomized sample of 106 participants, we will need to enroll one hundred and thirty-six (136) participants. With a randomized sample of 106 participants, our 80% confidence interval around the sample estimated variance will be within 18% of the true population variance and the conservative upper estimate of the variance will be used to inform the power of the larger R01. Primary AIM 2: Evaluate the efficacy of ABM combined with MET/CBT on cannabis outcomes in adults with CUD. Cannabis use will be measured by a combination of self-reported use days and (CN-THCCOOH) levels measured following the 4th week of treatment. The sample size of 53 randomized participants (42 completers) in each treatment group necessary to provide adequate power in Aim 1 will provide 80% power with a type 1 error rate of 5% to detect a similar effect size to Aim 2 ($d = 0.58$) in EOT (CN-THCCOOH) levels between study groups under similar model assumptions. The sample size of 42 completers per group will provide 80% power with a type 1 error rate of 5% to detect an 18% decrease in the proportion of use days in the ABM (39%) as compared to Sham (57%). Thus, a **total randomized sample size of n=106** participants will provide adequate power to address the clinically meaningful study aims in a statistically efficient manner.

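### Aim 1 names no primary visit, contrast or measure; its 84 evaluable participants fit an EOT/FU average that the analysis text does not specify, and the 80% claimed for EOT cannabinoid levels does not follow

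*Combined protocol and SAP*

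**What the plan says.** All references are to the combined protocol and SAP.

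- **Aim 1, analysis (D5, Study Aims).** The aim is stated as "Aim 1 is to evaluate the efficacy of ABM in the reduction of cannabis cue reactivity outcomes between BL and EOT/FU". A mixed model is fitted to the two post-treatment visits, and then "Model based means and associated standard errors will be used to assess treatment group differences at EOT and FU". Section A gives Hypothesis 1 no time point. D1 and D4.e list cue reactivity at baseline, EOT and FU without ranking the visits. Section A counts both skin conductance and craving as cue reactivity, also unranked.
- **Aim 1, power (D5, Statistical Power and Sample Size).** The effect d = 0.58 comes from pilot MCQ craving at end of treatment. The text adds that "we will measure use during the final treatment visit as well as at the FU visit" (it says use, although the aim is cue reactivity), assumes a correlated-measures model with correlation 0.8, and concludes that "a sample size of 84 participants would be necessary to detect the noted treatment effect size with 80% power". With 20% attrition this becomes 106 randomized, 53 per arm.
- **Aim 2, power (same section).** With 42 completers per arm, the plan claims the same 80% for a similar effect (d = 0.58) "in EOT (CN-THCCOOH) levels between study groups under similar model assumptions".
- **Aim 2, analysis (D5, Study Aims).** "Study data will be modeled as time invariant summary measures of the use at the end of the 4-week study period". Abstinence at FU is explicitly secondary. Aim 1 has no equivalent sentence.

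**The concern.** Two things do not line up.

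First, the Aim 1 sample size appears to belong to one contrast (a treatment effect pooled over EOT and FU), while the analysis text most naturally describes another (a difference at each visit). The power section does not say which contrast it covers.

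Second, the power section carries the same 42 per arm, d = 0.58 and 80% over to cannabinoid levels at EOT alone. There the plan has one end-of-period measure and no second visit to average.

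At stake is which result decides Aim 1, and whether the stated 80% applies to it. With two visits and two measures unranked, the deciding result could be settled after the data are seen. The estimate and its variance are also meant to power a larger trial, so the contrast to which d = 0.58 belongs needs to be on record.

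**Working it through.** **Inputs, from the D5 power section:** d = 0.58; correlation 0.8; power 80% (z = 0.8416); type 1 error 5%. Sidedness is not stated; two-sided is assumed (z = 1.96).

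**Reproducing 84.** For one visit without baseline adjustment, n per arm = 2 × (1.96 + 0.8416)² / 0.58² = 46.66, or 93.3 in total. Other contrasts multiply this by a variance factor:

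| Contrast | Variance factor | Total |
|---|---|---|
| Average of EOT and FU | (1 + 0.8)/2 = 0.90 | **84.0** |
| Single visit | 1 | 93.3 |
| Change from baseline, one visit | 2(1 − 0.8) = 0.40 | 37.3 |
| Baseline-adjusted, one visit | 1 − 0.8² = 0.36 | 33.6 |

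A one-sided single-visit test gives 37 per arm (74). An average of three measures gives 41 per arm (82), but the text names two visits. Only the EOT/FU average uses the two named visits and gives 84. For attrition, 42/0.8 = 52.5, so 53 per arm and 106 in total, as the plan states.

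**Power for Aim 1 at 42 per arm.**

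- Single visit: 0.58 × √(42/2) = 2.658; 2.658 − 1.96 = 0.698; power 75.7% (74.8% by t-test).
- Average: 2.658/√0.90 = 2.802; 2.802 − 1.96 = 0.842; power 80.0% (79.1% by t-test).
- Two unadjusted visit tests with correlation 0.8: the chance of at least one false positive is about 7.8%. Power is about 84% if either visit suffices and 68% if both are required.

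**EOT cannabinoid levels at 42 per arm, d = 0.58.**

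- No gain from baseline: 75.7%, as for any single measure.
- If 0.8 is the baseline correlation: 2.658/√0.36 = 4.43; 4.43 − 1.96 = 2.47; power 99.3%.
- Exactly 80% needs 1 − r² = (2.658/2.8016)² = 0.900, so r = 0.32 (0.35 by t-test). Without baseline gain it needs d = 2.8016 × √(2/42) = 0.61 (0.62 by t-test). The plan states none of these.

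**Baseline adjustment in general (single visit, d unadjusted).** For assumed correlations of 0.3 and 0.5, power is 79.6% and 86.6%.

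**If the effect fades by FU (assumed decay).** The average has less power than EOT alone once the FU effect is below 0.58 × (2√0.90 − 1) = 0.52. At FU effects of 0.435 (25% decay) and 0.29 (50% decay), averaged power is 69% and 56%, against 76% for EOT alone.

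**Pilot figures.** √(1.0² + 1.0²) = 1.41, so the ± values behave as standard errors. Then 3.7/1.4 = 2.64, with p about 0.01. Section C reports "Results showed a trend of blunted cannabis cue-induced craving at end of treatment among ABM participants compared to controls" with p = 0.051. These appear to come from different analyses, and the plan does not say whether d = 0.58 is baseline-adjusted.

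**The case against.** The strongest reply is that there is no contradiction in Aim 1. The power section names both visits and a correlated-measures model immediately before giving 84. The aim is written with EOT and FU joined by a slash, and one mixed model over both visits can deliver a pooled effect. On that reading 84 and 106 reproduce exactly. This stands: for Aim 1 the fault is ambiguity, and the plan still needs to say that the pooled effect is the contrast.

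Next, 76% is a floor. Cue reactivity is measured at baseline, and a baseline correlation of only 0.32 restores 80%. This also stands. However, D5 states control for the baseline response explicitly only for the neuropsychological data; for the aims, covariates are chosen by observed association with the outcome.

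Third, the cannabinoid claim rests on assumptions described only as similar, with no formula, and cannabinoid levels are collected at every visit. But the power text ties the outcome to EOT, after week 4, and the analysis text uses one summary at that point. The stated inputs then give about 76% or about 99%, depending on the role of 0.8, and neither is 80%.

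Finally, this is a pilot whose main purpose is preliminary data. That limits the consequences, but the plan nevertheless claims adequate power for its primary aims.

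**Conclusion.** The point holds as a gap in specification plus one unsupported power figure. Aim 1 has no primary visit, contrast or measure. The averaged contrast is inferred from the arithmetic (two-sided 5% assumed). If it is intended, the Aim 1 sample size is right. If the visits are to be tested separately without baseline adjustment, power is about 76% each, with about a 7.8% chance of a false positive at one or other visit. The 80% for EOT cannabinoid levels does not follow from the stated inputs on either reading of the correlation.

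Three stronger readings are not supported:

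- *The trial is underpowered or needs more participants.* The shortfall is about 4 points in the least favourable case, and modest baseline adjustment removes it.
- *The pilot effect is wrong.* Backing out standard deviations from the pilot standard errors is tempting, but these may be model-based, the pilot figure is not shown, and the test behind p = 0.051 is not described. Only a request for clarification is justified.
- *The 20% attrition invalidates the calculation.* The pilot reports that "39 (80%) completed all 4 study sessions, and 33 (67%) completed through follow-up", so 20% matches session completion rather than follow-up. Applying both rates to this trial's EOT and FU visits moves averaged power only from 80% to about 79%.

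**What to change.** In D5:

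1. Name cue-induced MCQ craving as the primary Aim 1 measure, and name one primary contrast. The EOT/FU average from the planned mixed model matches the existing sample size and keeps the stated 80%.
2. Report the visit-specific and skin-conductance results as secondary, with intervals.
3. If EOT is preferred as the primary visit, specify adjustment for baseline craving and give power over a range of baseline correlations, with about 76% as the unadjusted floor.
4. Restate power for EOT cannabinoid levels as about 76% at d = 0.58, or specify the baseline adjustment and correlation that give 80%.
5. State whether d = 0.58 is baseline-adjusted, and explain how the pilot difference and its standard error relate to p = 0.051.

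The cost is wording, with no added participants. Results not chosen lose primary status, and one power figure may become slightly less favourable. Choosing the average accepts less power than EOT alone if the FU effect is below about d = 0.52; choosing EOT gives up the gain from the second visit.

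### The 80% power stated for week-4 CN-THCCOOH comes from a two-measure average; an unadjusted week-4 contrast has about 75-76%, and the Aim 2 text leaves baseline adjustment and missing week-4 values open

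*Combined protocol and SAP*

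**What the plan says.** All references are to section D5 of the combined protocol and SAP unless stated.

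- **Data structure for Aim 2 (Study Aims):** "Study data will be modeled as time invariant summary measures of the use at the end of the 4-week study period".
- **Timing (Statistical Power and Sample Size):** "Cannabis use will be measured by a combination of self-reported use days and (CN-THCCOOH) levels measured following the 4th week of treatment". The power claim that follows is for end-of-treatment (EOT) levels.
- **Text pointing the other way (Study Aims):** "Aim 2 is to evaluate the efficacy of ABM on the reduction of cannabis use characteristics between BL and EOT/FU". The abbreviation GLM is also introduced as a generalized linear mixed model.
- **Analysis set (General Analysis):** "All analyses will be performed on the intent-to-treat sample consisting of all randomized subjects".
- **Covariates (General Analysis):** "Characteristics found to be significantly associated with the primary outcome measures, will be included as covariates in the initial stages of adjusted model development". Baseline control is written out only for the neuropsychological data: "between group comparisons taken at EOT and FU visits while controlling for baseline response data".
- **Stratification (Randomization):** "The randomization will be stratified on (1) gender and (2) baseline daily cannabis use intensity".
- **Basis of the power (Aim 1):** "we will measure use during the final treatment visit as well as at the FU visit", with a within-person correlation of 0.8. The Aim 2 paragraph then states 80% power for EOT CN-THCCOOH at the same d of 0.58, on model assumptions described as similar.
- **Missing data:** the one remark on this, that the mixed models cope well with it, sits in the Aim 1 text.

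Section D1 says cannabinoid levels are collected at every visit, and D4.f says urine samples go to the laboratory for quantification.

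**The concern.** This point concerns CN-THCCOOH only; the timeline follow-back outcomes summarise days and raise different questions.

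Two things do not fit together. First, the 80% power belongs to an average of two correlated occasions, while the outcome it is attached to is a level at one occasion. Second, if each person contributes one response, a mixed model has nothing to use for someone whose week-4 urine is missing. An analysis said to include everyone randomized then becomes an analysis of those with a week-4 sample, although earlier cannabinoid values exist for many of the others.

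At stake are a few points of power on a primary outcome, collected data left unused, and a primary model whose baseline term depends on a significance test in the trial data.

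**Working it through.** **Inputs (section D5, power paragraph):** d = 0.58; type 1 error 5%, taken as two-sided because that reproduces the plan's figure; power 80%; correlation 0.8; 53 randomized and 42 completers per arm; attrition 20%.

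**Formulas:** n per arm = 2f(1.960 + 0.842)²/d², and power = Φ(d√(n/(2f)) − 1.960). Here f is the variance of the analysed quantity relative to one value. Noncentral-t results are marked t.

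1. **Reproduce the plan.** For the mean of two measures, f = (1 + 0.8)/2 = 0.9. Then n = 2 × 0.9 × 7.849/0.3364 = 41.998, so 42 per arm and 84 in total. Power at 42 is 80.0% (t: 79.1%). Attrition: 42/0.8 = 52.5, so 53 per arm and 106. The plan's figures reproduce.

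2. **One week-4 value, unadjusted.** f = 1, so n = 2 × 7.849/0.3364 = 46.66, or 47 per arm (t: 48). At 42 per arm, 0.58 × √21 = 2.658, and Φ(2.658 − 1.960) = 75.7% (t: 74.8%). Detectable d at 80% power is 2.802 × √(2/42) = 0.611 (t: 0.619).

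3. **EOT contrast from a treatment-by-visit model on EOT and follow-up.** With complete data and no baseline term, the EOT contrast has the variance of a single value, so f = 1 and power is as in step 2. The factor 0.9 applies only when the effect is averaged over both visits.

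4. **Baseline adjustment.** f = 1 − r², where r is the correlation of baseline with week-4 CN-THCCOOH. The documents give no value for r, so a range is shown. Setting 1 − r² = 0.9 gives r = 0.316 for 80% power (t: 0.348).

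| Assumed r | Power, normal | Power, t |
|---|---|---|
| 0.2 | 77.4% | 76.4% |
| 0.3 | 79.6% | 78.6% |
| 0.4 | 82.6% | 81.7% |
| 0.6 | 91.3% | 90.7% |
| 0.8 | 99.3% | 99.2% |

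5. **Baseline admitted only if significant.** Simulation with 42 per arm, d = 0.58 and 40,000 replicates, admitting baseline when its correlation with the outcome has p < 0.05. At r = 0.2, 0.3, 0.35 and 0.4, baseline enters in 42%, 76%, 89% and 96% of trials, and power is 75%, 78%, 79% and 81%.

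6. **People without a week-4 value.** 53 − 42 = 11 per arm, or 22 of 106, if the planned attrition equals missing week-4 values. The pilot's 80% in section C (39/49) counts completion of all four sessions, so fewer may be missing. With 10%, 20% or 30% missing (48, 42 or 37 per arm), unadjusted power is 80%, 75% or 69% (t).

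**The case against.** **The model may be the two-measure one.** The Aim 2 power is said to rest on assumptions like those of Aim 1, and Aim 2 opens by mentioning both EOT and follow-up. On that reading repeated values were intended. This has some force, and the one-value reading is not certain. It does not rescue the 80%, because the claim is for EOT levels and step 3 shows that an unadjusted EOT contrast from that model still has f = 1.

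**The mixed models are said to handle missing data.** The remark appears under Aim 1. It cannot help a model with one response per person.

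**Baseline would probably enter anyway.** If baseline correlates with week 4 at 0.5, the significance screen admits it in 99.6% of simulated trials and power is 86%; at 0.8 it always enters and power is 99%. This stands: the shortfall vanishes at moderate correlations. But the documents give no such correlation for CN-THCCOOH, and a primary model should not depend on the screen.

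**The trial is a pilot and the loss is small.** Also true, although the plan claims adequate power for its primary aims.

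**A stronger reading about bias.** A reader might infer that the analysis will give a biased result or an inflated false-positive rate. Simulations can produce this. With 20% loss, and dropout log-odds rising by 1 per SD of the last value in one arm only, null bias is about 0.11-0.15 SD and total type 1 error 8-11%. Those inputs are assumed. Nothing in the documents suggests that such dropout will occur, or in which arm, and the same mechanism in both arms gives no null bias. The figures illustrate why a sensitivity analysis is worthwhile and carry no further weight.

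**Conclusion.** The point holds, with limits. The stated 80% for EOT CN-THCCOOH is not supported by the model it is taken from. Without baseline adjustment, power at 42 per arm and d = 0.58 is about 75-76%, a shortfall of 4 to 5 points, whether the contrast comes from one value or from a treatment-by-visit model with complete data. With baseline adjustment and a correlation of about 0.32-0.35 or more, 80% is reached or exceeded.

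The conflict with the all-randomized analysis set depends on the one-value reading, which is the more natural one but not the only one. The count of about 22 depends on equating planned attrition with missing week-4 urine.

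A reader might also infer that the trial is too small. The documents do not support that: the sample size reproduces for Aim 1, and a prespecified baseline term could more than make up the loss for this outcome. This should be corrected, but it does not undermine the design.

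**What to change.** 1. Name baseline CN-THCCOOH and the two randomization strata (gender and baseline use intensity) as fixed covariates in the Aim 2 CN-THCCOOH model, not selected by significance.
2. Fit the mixed model to all post-baseline CN-THCCOOH values already collected, on a suitable scale such as log, with treatment, visit and treatment-by-visit, and keep week 4 as the primary contrast. Anyone with at least one post-baseline value then contributes. Add a missing-data sensitivity analysis covering all 106, for example multiple imputation with dropouts' week-4 values shifted over a stated range, separately by arm.
3. Restate the power for the model actually used: about 75-76% if unadjusted, otherwise with the assumed baseline correlation given. Nearly all the precision gain comes from baseline (standard error 0.21-0.22 SD unadjusted against 0.13-0.19 with baseline or all visits in the simulations), so the restated figure should rest on that term.

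The cost is a few sentences of plan wording and a little more analysis work, with no new visits, samples or participants. The primary model will rely on a missing-at-random assumption and will still omit anyone with no post-baseline value; the sensitivity analysis is there to probe both.
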